**Pulmonary arterial hypertension**

**Protocol AC-065A203**

**Confidential**

**Amendment 7 Version 8**

30 September 2021, page 84/154

Period	Site visits for participants during the first 12 months following Week 16 (M4)	Site visits for participants after 12 months	Phone calls for participants after 12 months	Unscheduled visit	End-of-Treatment	Safety follow-up Tel.
Name	Visit 9, 10, 11, 12	Visit 13, 14, 15 ...	Tel.	Unscheduled visit	EOT	EOS
Time e	Site visits every 3 months (M7, M10, M13, M16) ± 15 days	Site visits every 6 months (M22, M28, M34...) ± 15 days	Phone call: every 6 months (M19, M25, M31, M37...) alternating with visits ± 15 days	If medically indicated or recommended for assessing PAH progression	Last dose of study drug + up to 7 days	Phone call: 30 days after last dose of study drug + up to 7 days
Palatability and acceptability of selexipag					X	
(Serious) adverse events	X	X	X.	X	X	X
Vital status						X

- a. Urine pregnancy tests to be performed monthly, and results to be communicated to site staff by telephone.
- b. Only at Month 7 / Visit 9.
- c. Physical exam only for areas of interest (general appearance, cardiovascular, and respiratory system).
- d. Echo to be done at Month 7 only.
- e. One month corresponds to 4 weeks/28 days.

6MWD 6 minute walk distance; appl. applicable; ECG electrocardiogram; EOS End of Study; EOT End of Treatment; FC functional class; M month; Mod. modified; NT pro BNP N terminal pro b type natriuretic peptide; NYHA New York Heart Association; PAH pulmonary arterial hypertension; Tel. telephone call; TSH thyroid stimulating hormone; WHO FC World Health Organization functional class.

Confidential

## 7.2 Study assessments

The study assessments are listed in [Table 4](#) and [Table 5](#). The assessments to be performed during each visit are marked with an 'X'.

All study assessments are performed by qualified study personnel (medical, nursing, or specialist technical personnel) and are recorded in the eCRF, unless otherwise specified. Study assessments performed during unscheduled visits will also be recorded in the eCRF. The following order of assessments is recommended: PK samples, safety assessments, efficacy assessments, other assessments (unless otherwise specified in [Table 4](#) and [Table 5](#) and in the assessment descriptions below).

If the principal investigator (PI) delegates any study procedure/assessment for a participant, eg, blood sampling to an external facility, they should inform the Sponsor to whom these tasks are delegated. The set-up and oversight will be agreed upon with the Sponsor. The supervision of any external facilities remains the responsibility of the PI.

Calibration certificates / evidence of equipment maintenance for the below-listed equipment used to perform study assessments must be available prior to the screening of the first participant:

- Body weight scale
- Temperature measurement devices for study treatment storage area and freezer.

Calibration certificates / evidence of equipment maintenance of other equipment should be available as per local requirements.

### 7.2.1 Demographics / baseline characteristics

Demographic and baseline characteristic data to be collected on all participants include: age, sex, race, and ethnicity. Relevant medical history / current medical conditions (eg, chronic and ongoing acute conditions, serious past conditions) present before signing the ICF will be recorded on the medical history page. Where possible, diagnoses and not symptoms will be recorded. The presence/absence of Down syndrome is recorded for all participants in the eCRF.

Medical history of special interest will be captured on the specific Medical History eCRF page and includes:

- Disease characteristics such as PAH etiology, PAH diagnosis (mPAP, PAWP [or LAP, or LVEDP], PVRi values assessed by RHC, and date of diagnosis), date of first observed / assumed PAH symptoms, and signs and symptoms of PAH.
- Medical history (previous and ongoing clinically significant diseases).

For participants who failed screening, the following data will be recorded in the eCRF if available:

- Reason for screening failure.
- Baseline data collected until confirmation of screening failure.
- If baseline data are available from any central laboratory (eg, physical activity) they will be transferred to the clinical database.

## **7.2.2 Exploratory assessments**

### **7.2.2.1 Monitoring of disease progression – signs and symptoms of PAH**

To standardize assessment of disease progression, investigators will verify the presence/absence of predefined signs and symptoms denoting clinical worsening of PAH.

The presence and absence of signs/symptoms as well as date of new onset or worsening is recorded in the eCRF.

If there is syncope or at least 2 new or worsening signs/symptoms the investigator reports disease progression in the eCRF and performs further exams to determine the cause [refer to Section 7.1.2]. In addition, the occurrence of a new or worsening sign/symptom is reported as Adverse Event in the eCRF.

### **7.2.2.2 WHO functional class**

The WHO FC [see Section 14.1 Appendix 1] and the Panama FC [Section 14.2 Appendix 2] are recorded in the eCRF. The Panama FC is tailored for children up to 16 years of age [Lammers 2011] and thus its assessment will discontinue in children > 16 years of age.

### **7.2.2.3 NT-proBNP**

The quantification of NT pro-BNP plasma levels will be performed by the central laboratory [see contact details on page 2]. Central laboratory data will be automatically transferred from the central laboratory database to the clinical database.

The materials required for NT pro-BNP sampling will be provided to the investigational site before the start of the study.

The procedure for the collection and analysis of NT pro-BNP is described in the respective Laboratory Manual.

The actual date and clock time of withdrawal of each blood sample is to be entered in the eCRF.

NT pro-BNP central laboratory reports will be sent to the investigator.

Confidential

#### 7.2.2.4 6-minute walk distance test

The 6MWD test will be performed in children from  $\geq 6$  to  $< 18$  years able to understand and perform the test correctly [Takatsuki 2013, Douwes 2015].

The 6MWD test is performed and recorded in the eCRF, as indicated in the assessment schedule. The time of the assessment will be recorded in the eCRF.

The 6MWD is a non-encouraged test that measures the distance covered by the participant during a 6-minute walk.

#### 7.2.2.5 Echo/Doppler

Echo/Doppler will be performed at the visits indicated in the assessment schedule and as described in the guidelines and the central reader manual provided separately from this protocol.

The following Echo/Doppler parameters will be measured:

- Right ventricular systolic pressure.
- Tricuspid annular plane systolic excursion.
- Pulmonary artery acceleration time.
- Left ventricular eccentricity index.
- Right atrial area index (from apical 4 chamber view).
- Tricuspid annular diameter (from apical 4 chamber view).

Echo/Doppler data are analyzed centrally and will not be recorded in the eCRF.

#### 7.2.2.6 Palatability and acceptability

The palatability of the selexipag formulation will be assessed at the visits indicated in the assessment schedule using a 5-point facial hedonic scale.

For children not able to comply with the instructions of the test, palatability will be indirectly assessed by the participant's parent(s) or LAR(s) or study site personnel [see Section 14.3 Appendix 3].

The site study personnel will record the palatability score corresponding to the smiley face pointed to by the participant or the response provided by participant's parent(s) or LAR(s) or study site personnel in the eCRF.

The acceptability of the selexipag formulation will be assessed through a 3-point categorical scale as to whether the child swallowed the medication at the visits indicated in the assessment schedule.

For all participants, parent(s) or LAR(s) or study site personnel will be asked, following the study drug intake, whether the child swallowed the medication:

- a. fully,
- b. partially,
- c. not at all.

The site study personnel will record the acceptability score corresponding to the response provided by participant's parent(s) or LAR(s) or study site personnel in the eCRF and source documents.

### **7.2.3 Safety assessments**

The definitions, reporting, and follow-up of AEs, SAEs, and pregnancies are described in Section 9.

#### **7.2.3.1 Physical examination**

Complete physical examination at screening includes the examination of:

- General appearance.
- Head, ears, eyes, nose, throat.
- Cardiovascular.
- Respiratory.
- Gastrointestinal.
- Lymphatic.
- Genitourinary.
- Skin.
- Extremities.
- Nervous system.

At subsequent visits, physical examination includes the examination of general appearance and cardiovascular and respiratory systems.

Other exams will be performed if indicated, based on medical history and/or symptoms.

Information for all physical examinations must be included in the source documentation at the study site. The observations should be reported according to body system in the eCRF as either normal or abnormal. If an abnormality is found it should be specified on the corresponding eCRF page.

Clinically relevant findings that are present prior to the signing of the ICF must be recorded on the Medical History eCRF page.

Physical examination findings made after the signing of the ICF that meet the definition of an AE [Section 9.1.1] must be recorded on the AE page of the eCRF.

#### **7.2.3.2 Vital signs**

Vital signs include systolic and diastolic BP and heart rate. Vital signs are measured non-invasively. It is recommended that vital signs are measured after the participant has rested at least 5 minutes (eg, sitting). If applicable, vital signs are measured before any invasive assessment (such as blood draw).

Systolic and diastolic BP will be measured in a supine or sitting position. It is recommended to allow the participant to rest for at least 5 minutes, and to use the same position (supine or sitting) throughout the study for an individual participant.

It is recommended that the same type of device is used throughout the study for an individual participant. In addition, blood pressure is measured on the same arm for an individual participant throughout the study.

Vital signs are recorded in the eCRF.

#### **7.2.3.3 ECG**

A standard 12-lead ECG is performed at Baseline/Enrollment, Visit 3 (only for participants who have PK sampling), Visit 5, Visit 7 (only for subjects who have PK sampling), Visit 8, Visits 9, 10, 11, 12, 13, 14, 15, etc., and EOT. The participant should rest for at least 5 minutes prior to the recording, and should be in a supine position during the recording. The ECG should be performed before the morning dose of study drug is taken.

At Visit 3 or Visit 7, participants will have two additional ECGs 2 and 4 hours ( $\pm 15$  min) after study drug morning dose intake.

Clinically relevant ECG findings that are present prior to the initiation of study drug must be documented in the Medical History section of the eCRF.

Clinically relevant ECG findings observed after study drug initiation that were not present at Screening or that worsened during the study must be reported as AEs as appropriate [see Section 9.1.1].

A central ECG service [see contact details on page 2] will be used for ECG evaluation. Details about the collection of ECG data and the reporting of results and abnormalities can be found in the ECG manual provided to the investigator.

#### **7.2.3.4 Weight and height**

Height will be measured using a stadiometer at Screening and at Week 16, every 3 months for 1 year following Week 16, then every 6 months. Body weight will be measured in indoor clothing but without shoes.

Confidential

Body weight and height are measured and recorded in the eCRF.

#### **7.2.3.5 Tanner stage**

Per CHMP Paediatric addendum to the PAH guidelines [[EMA/CHMP/213972/2010](#)], the sexual maturation of pediatric participants in long-term studies is of particular importance. Therefore, the Tanner stage [refer to Section [14.5 Appendix 5](#)] is assessed at regular time points during the study.

Tanner stage is assessed in female participants  $\geq 8$  years of age and in male participants  $\geq 9$  years of age (i.e., examination is started once they are 8 and 9 years old, respectively). For participants who enter the study below these ages, sexual maturity assessments will start once they reach the ages of 8 or 9 years (for girls and boys, respectively). Tanner stage assessment is stopped once full sexual maturation is reached (if applicable before EOT). (Self-)Assessment of pubertal Tanner stage by parents or participants may be allowed by the study investigator. In this case, the investigator instructs and assists parents / participants on how this should be assessed at each time of the scheduled assessment.

The Tanner stages of puberty in girls are based on breast size and shape and pubic hair distribution. The Tanner stages of puberty in boys are based on the development of the genitalia and pubic hair distribution [[Blondell 1999](#), [Marshall 1969](#), [Marshall 1970](#)]. Actual age at milestone attainment may vary among individuals and among different study populations.

The site study personnel will record the Tanner stage in the eCRF.

For frequency of Tanner stage assessments, see schedule of assessments in [Table 4](#) and [Table 5](#).

#### **7.2.3.6 Childbearing potential**

Childbearing potential will be assessed at each visit and recorded in the eCRF.

For female participants of childbearing potential, the study personnel will verify at each visit whether the participant has or plans to become heterosexually active. If confirmed, the study personnel will counsel the participant on the appropriate methods of contraception [refer to Section [4.5.2](#)].

The reason for not being of childbearing potential will be recorded in the eCRF.

### **7.2.4 Laboratory assessments**

#### **7.2.4.1 Type of laboratory**

A central laboratory [see central laboratory manual for contact details, page [2](#)] will be used for all protocol-mandated laboratory tests, including re-tests due to laboratory abnormalities and laboratory tests performed at unscheduled visits.

If the results from the central laboratory are not available in time for enrollment of the participant, an additional blood sample may be drawn to verify eligibility based on a local laboratory test. The local laboratory results (with the corresponding normal ranges) must be recorded in the eCRF.

Other exceptional circumstances that require the recording of local laboratory results of the parameters are described in Section 7.2.4.2 (with corresponding normal ranges), including hospitalization of the participant due to a medical emergency and missing central laboratory results from a scheduled or unscheduled visit.

If one or more central laboratory samples are lost or cannot be analyzed for whatever reason, the investigator will collect an additional sample as soon as possible to repeat the analysis, unless a local laboratory sample was collected within the same time-window and these test results are available.

After Week 16, under specific circumstances (eg, if the participant lives far from the site and cannot return to the site), laboratory samples may be collected at a laboratory close to where the participant lives (satellite laboratory) and sent to the central laboratory for analysis. In such cases, the satellite laboratory must be provided with the central laboratory sampling kits. Shipment of the samples will be organized by the satellite laboratory. If this process is implemented, the satellite laboratory must be identified prior to enrollment of the participant in the study. The supervision of the satellite laboratory remains the responsibility of the PI.

Central laboratory reports will be sent to the investigator. In the case of specific (pre-defined) laboratory abnormalities, the central laboratory will alert the Sponsor personnel and the concerned site personnel. Alert flags that will trigger such notifications are displayed in the central laboratory manual, provided separately.

All laboratory reports must be reviewed, signed, and dated by the investigator or delegate within 10 working days of receipt and filed with the source documentation. The investigator/delegate must indicate on the laboratory report whether abnormal values are considered clinically relevant or not. Clinically relevant laboratory findings that are known at the time of the signing of the ICF must be recorded on the Medical History page of the eCRF. Any clinically relevant laboratory abnormalities detected after signing of informed consent must be reported as an AE or SAE as appropriate [see Section 9], and must be followed until the value returns to within the normal range or is stable, or until the change is no longer clinically relevant.

Details about the collection, sampling, storage, shipment procedures, and reporting of results and abnormal findings can be found in the laboratory manual.

### 7.2.4.2 Laboratory tests

#### Hematology

- Hemoglobin (g/L)
- Hematocrit (L/L)
- Erythrocyte count ( $10^9/L$ )
- Leukocyte count with differential counts ( $10^9/L$ )
- Platelet count ( $10^9/L$ )

#### Clinical chemistry

- Alanine aminotransferase (U/L)
- Aspartate aminotransferase (U/L)
- Alkaline phosphatase (U/L)
- Total and direct bilirubin ( $\mu\text{mol/L}$ )
- Creatinine ( $\mu\text{mol/L}$ )
- Creatinine clearance (mL/min)
- Blood urea nitrogen (mmol/L)
- Uric acid ( $\mu\text{mol/L}$ )
- Glucose (mmol/L)
- Cholesterol, triglycerides (mmol/L)
- Sodium, potassium, chloride, calcium (mmol/L)
- Albumin (g/L)
- NT-pro BNP (pmol/L)
- TSH (mU/L)
- Thyroid antibodies (U/mL): Measured at Baseline/Enrollment and at subsequent visits only if TSH is abnormal or when medically indicated
- Free T3 and free T4: Measured only if TSH is abnormal or when medically indicated

Up to Week 16, a total of approximately 24 mL of blood are required for hematology and clinical chemistry testing. After Week 16, approximately 4.8 mL of blood are required per visit.

#### Pregnancy test

A serum pregnancy test for females of childbearing potential will be performed at Screening and a urine test will be performed on Day 1 (Baseline/Enrollment) before dosing and monthly thereafter. If pregnancy is suspected during the study, a serum pregnancy test

must be performed immediately. Results of the urine pregnancy tests performed after Day 1 are not collected in the eCRF.

## 7.2.5 Pharmacokinetic assessments

### 7.2.5.1 Pharmacokinetic assessments

PK blood sampling will be done:

- During the first week of study treatment (PK samples will be collected in the first 5 participants treated in Cohorts 1 to 3 at the following time points: pre-dose, 1, 2, 4, 6, 8, and 12 hours post-morning dose of selexipag (participants should have been on the same dose and mode of administration for at least 3 days in order to reach steady state).
- During the up-titration period,  $C_{\text{trough,ss}}$  PK samples will be collected in all participants prior to dose escalation at Day 15, and Weeks 4 and 6 (participants should have been on the same dose and mode of administration for at least 3 days in order to reach steady state).
- In each cohort, for participants who did not provide samples during the first week of study treatment, PK samples will be collected at Week 12 at steady state at the following time points: pre-dose, 1, 2, 4, 6, 8, and 12 hours post-morning dose of selexipag (participants should have been on the same dose and mode of administration for at least 3 days in order to reach steady state).

For the participant's convenience, an overnight stay at the site may be required before and/or after the PK profile sampling visit.

In total, 10 PK samples (1.2 mL blood/sample) will be collected per participant. The total amount of blood collected from each participant will be 12 mL. This is in accordance with general recommendations that the total blood volume collected within 24 hours for the purpose of a trial in children should not be more than 1%–5% of total body blood volume. Children are assumed to have 75–80 mL blood / kg body weight; i.e., a 9 kg infant is considered to have approximately 720 mL of total blood volume.

Blood sampling will take approximately 1 minute. [Table 4](#) displays the time points at which the PK samples will be taken.

### 7.2.5.2 Instructions regarding meals

On the day of the PK samples collection (at Visit 3 or Visit 7 and at Visits 4, 5, and 6), the participant's parent(s)/LAR(s) will be instructed that the meal preceding the morning and evening dose should be light.

Dates and time of meals preceding PK samples will be recorded in the eCRF.

Confidential

### 7.2.5.3 Procedure for sampling

To prevent the degradation of selexipag and its metabolites in plasma samples, exposure of the plasma to light should be minimized and the whole sample preparation should be conducted under yellow light.

Blood samples of 1.2 mL will be collected by direct venipuncture or via an i.v. catheter in spray-dried lithium heparin-containing Greiner Vacuettes®. Immediately following collection, the tube will be slowly tilted backwards and forwards (no shaking) to bring the anti-coagulant into solution and immediately cooled on ice. Within 30 minutes of collection, the blood samples will be centrifuged at approximately 1500 × g / 3000 revolutions per min for 10 minutes, preferably at 4 °C (39.2 °F).

The resulting plasma (approximately 0.5 mL plasma) will be transferred into a single, labeled, opaque polypropylene tube to avoid carryover of erythrocytes.

All samples will be stored in an upright position at ≤ 18 °C ( 0.4 °F).

The date and exact actual clock time of collection of each blood sample will be entered in the eCRF.

For additional details, refer to the laboratory manual.

### 7.2.5.4 Labeling

The tubes and labels will be provided by the central laboratory. The tubes for PK assessments will be pre-labeled and will carry the following information:

- Actelion Pharmaceuticals Ltd
- Study number: AC-065A203
- Selexipag and ACT-333679
- Type of sample: plasma
- Visit number (eg, Visit 3, Visit 7)
- Scheduled time point (eg, pre-dose, 1 hour post-dose)
- Participant number (eg, 2001 001)

### 7.2.5.5 Bioanalysis

The concentrations of selexipag (ACT-293987) and ACT-333679 will be determined using a validated liquid chromatography-tandem mass spectrometry assay. The foreseen limit of quantification for both analytes is 0.01 ng/mL. Concentrations will be calculated by interpolation from a calibration curve.

Quality control samples will be used to determine between-run and overall precision and accuracy of the analysis.

#### **7.2.5.6 Shipping procedures**

The site staff will be responsible for the shipment of the samples. Samples must be sent to the central laboratory [see contact details on page 2] at time intervals defined in the laboratory manual. The samples, together with the completed shipment forms, must be packed securely in polystyrene insulated shipping containers containing enough dry ice to last for 48 hours.

## **8 STUDY COMPLETION AND POST-STUDY TREATMENT / MEDICAL CARE**

### **8.1 Study completion as per protocol**

For an individual participant, study completion is reached when the EOS follow-up telephone call is completed.

### **8.2 Premature withdrawal from study**

Participant's parent(s)/LAR(s) may voluntarily withdraw their child from the study without justification for any reason at any time. Upon reaching his/her legal majority, the participant may also voluntarily withdraw from the study. Participants are considered to be withdrawn if they state an intention to withdraw further participation in all components of the study (i.e., withdrawal of consent), die, or are lost to follow-up. If a participant withdraws consent, no further data will be collected in the eCRF from the date of withdrawal onward. The investigator may withdraw a participant from the study (without regard to the participant's consent) if, on balance, they believe that continued participation in the study would be contrary to the best interests of the participant. Withdrawal from the study may also result from a decision by the Sponsor for any reason, including premature termination or suspension of the study.

Participants are considered to be lost to follow-up if all reasonable attempts by the investigator to communicate with the individual and/or their parent(s)/LAR(s) fail. The site must take preventive measures to avoid a participant being lost to follow-up (eg, document different ways of contact such as telephone number, home address, email address, person to be contacted if the participant cannot be reached). If the participant cannot be reached, the site must make a reasonable effort to contact the participant or their parent(s)/LAR(s), document all attempts in the source documents, and enter the loss of follow-up information into the eCRF. The following methods must be used: at least three telephone calls must be placed to the last available telephone number and one registered letter must be sent by post to the last available home address. Additional methods may be acceptable if they are compliant with local rules/regulations (eg, a visit by site personnel to the participant's

home), respecting the participant's right to privacy. If the participant is still unreachable after all contact attempts listed above, they will be considered to be lost to follow-up.

If premature withdrawal occurs for any reason, the reason (if known) for premature withdrawal from the study, along with who made the decision (participant, investigator, or Sponsor personnel) must be recorded in the eCRF, if known.

If, for whatever reason (except death or loss-to-follow-up), a participant is withdrawn from the study, the investigator should make efforts to schedule a last appointment / telephone call to assess the safety and well-being of the participant, collect unused study treatment, and discuss follow-up medical care. Data obtained during this last appointment / telephone call will be recorded in the participant's medical records but will not be collected in the eCRF. The investigator must provide follow-up medical care for all participants who are prematurely withdrawn from the study, or must refer them for appropriate ongoing care, as described in Section 8.4.

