### **9.1.4 Reporting of adverse events**

All AEs with an onset date after the signing of the ICF and up to EOS must be recorded on specific AE pages of the eCRF.

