### 9.2.2 Reporting of serious adverse events

All SAEs occurring after the signing of the ICF up to 30 days after study treatment discontinuation must be reported on AE pages in the eCRF and on an SAE notification

form, regardless of the investigator-attributed causal relationship with study treatment or study-mandated procedures.

An SAE is defined as related to protocol-mandated procedures if it appears to have a reasonable possibility of a causal relationship to either the study design or to protocol-mandated procedures (eg, discontinuation of a participant's previous treatment during a washout period, leading to exacerbation of underlying disease).

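### Section 8.2 keeps last-contact data out of the eCRF even when the investigator or sponsor ends a child's participation, which conflicts with the AE and SAE recording rules

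*Protocol*

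**What the plan says.** Protocol Section 8.2 has two rules on data after withdrawal.

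- The first depends on consent: "If a participant withdraws consent, no further data will be collected in the eCRF from the date of withdrawal onward".
- The second is wider. It opens "If, for whatever reason (except death or loss-to-follow-up), a participant is withdrawn from the study" and asks the investigator to try to arrange a last appointment or call, to check on the child, recover unused drug and discuss later care. What is learned there "will be recorded in the participant's medical records but will not be collected in the eCRF".

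Between the two, 8.2 names two withdrawal routes that do not start with the family. For the first it says "The investigator may withdraw a participant from the study (without regard to the participant's consent"), on the ground that staying in would harm the child's interests. For the second it says "Withdrawal from the study may also result from a decision by the Sponsor for any reason", and premature termination of the study is given as an example.

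The recording rules make no exception for withdrawn children. Section 9.1.4 says "All AEs with an onset date after the signing of the ICF and up to EOS must be recorded" on eCRF AE pages. Section 9.2.2 says that all SAEs from the signing of the ICF "up to 30 days after study treatment discontinuation must be reported on AE pages in the eCRF", and also on an SAE form.

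**The concern.** A bar on eCRF entry is right when the family or the participant has withdrawn consent. It has no such basis when the investigator or the sponsor takes the decision. The protocol gives no other reason for leaving those data out.

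For an AE first heard of at the last contact with such a child, a site cannot follow both 8.2 and 9.1.4, and for an SAE it cannot follow both 8.2 and 9.2.2. Neither document says which rule prevails. Nor do they say whether the last contact replaces the EOT visit and the 30-day call or is additional to them.

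Safety and tolerability is the secondary objective, so a recording rule that can leave out AEs matters. Any loss could be informative, because an investigator withdraws a child on a judgement about that child's welfare.

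**Working it through.** The plan gives no figure to reproduce here. The check compares the rules and then sizes the possible gap.

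**1. Who falls under which rule (Protocol 8.2, 9.1.4, 9.2.2)**

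| Route out of the study | Consent to data collection withdrawn? | Consent-based stop | Last-contact bar | 9.1.4 / 9.2.2 require entry |
|---|---|---|---|---|
| Consent withdrawn | Yes | Applies | Applies | Yes, no exception stated |
| Investigator decision | No | Does not apply | Applies | Yes |
| Sponsor decision | No | Does not apply | Applies | Yes |
| Death or loss to follow-up | Not relevant | Does not apply | Excepted | Yes, for what is known |

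The conflict without a reason behind it lies in the investigator and sponsor rows.

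**2. Which events are exposed**

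SAP Section 4.1 counts TEAEs up to EOT + 3 days. The general conventions in SAP Section 7 set EOT as the last day of drug intake. An AE that began on treatment but is first reported at the last contact therefore belongs in the TEAE tables. Two cases follow.

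- *The EOT visit is held and entered.* Protocol 7.1 places it within 7 days of the last dose, and Table 5 has AEs collected there. If it falls on the day of the last dose, at most the 3 days after it remain uncovered. Almost nothing is lost.
- *The last contact takes the place of the EOT visit.* Any AE that began after the previous scheduled contact and by EOT + 3 days may be missing. AEs from then to EOS may also go unrecorded.

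**3. Length of the exposed interval in the second case (Tables 4 and 5; a month is 28 days)**

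- From Week 12 to Week 16, AE contacts are 14 days apart, or up to 14 + 3 + 3 = 20 days using both visit windows. They are weekly or nearly so for most of the time before that.
- After Week 16, AE contacts (visits or calls) are 3 × 28 = 84 days apart, or up to 84 + 15 + 15 = 114 days.

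**4. What one missed child does to a table**

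Withdrawn children stay in the Safety Analysis Set, so a lost event reduces the numerator while the denominator is unchanged. Taking the planned enrolment of about 60, or about 20 per age cohort:

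- one child: 1/60 = 1.7 percentage points overall, 1/20 = 5 points within a cohort;
- two children: 2/60 = 3.3 points overall, or 2/20 = 10 points if both are in one cohort.

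These counts are assumptions. The documents give no number of investigator or sponsor withdrawals, and zero is possible. A percentage for a given term changes only if that child has no earlier recorded occurrence of it.

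**The case against.** The case for leaving 8.2 alone has five parts, and most of it stands as a limit on size.

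- **Stopping treatment is not withdrawal.** Protocol 5.1.9 has the investigator stop treatment when it no longer serves the child. It says that such a child remains in the study and is followed for safety for 30 days. Section 7.1 adds the EOT visit, at which Table 5 marks AEs, vital signs, laboratory tests, ECG and accountability. A child stopped for an AE would normally take this route.
- **The affected group is narrow.** Sections 5.1.9 and 8.2 describe withdrawn participants mainly as those who withdraw consent, die or are lost. Investigator and sponsor withdrawals are what remains.
- **SAEs are protected.** Sections 9.2.2 and 9.2.5 send every SAE to the sponsor on a form within 24 hours. Section 8.2 does not touch that.
- **Laboratory and ECG data do not depend on the eCRF.** Section 11.3 has central laboratory and ECG results sent electronically to the sponsor. The last contact may be only a call and prescribes no test.
- **Nothing already entered is removed.** Every dosed child stays in the Safety Analysis Set.

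A reader might infer that safety events in these children drop out of the analysis, or that laboratory and ECG abnormality rates are biased downward. The points above rule out both as general statements.

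They do not settle the contradiction. The last contact overlaps the EOT visit in content (safety check, drug return), so a site could reasonably treat it as the substitute and enter nothing. The SAE form does not capture non-serious AEs, which make up much of the tolerability profile described in 5.1.10.

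**Conclusion.** The point holds as a conflict between stated rules with a probably small effect. Section 8.2 bars eCRF entry for investigator and sponsor withdrawals without a consent reason, against 9.1.4 and 9.2.2.

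The likely loss is confined to AEs, mostly non-serious, that are first learned at the last contact and began by EOT + 3 days, together with AEs after that up to EOS. It rests on two assumptions: that such withdrawals occur, and that the last contact stands in for the EOT visit. If the EOT visit is held and entered, the TEAE tables lose almost nothing.

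A reader might also infer that ending the study early would remove the final safety contact of every child still in it. The documents do not support that. Section 8.2 names termination as a withdrawal route, but 5.1.9 lists it as a reason for stopping treatment, which brings the EOT visit and 30-day follow-up. Section 8.3 requires appropriate follow-up and allows the sponsor to add procedures. The texts are ambiguous on this and go no further.

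The correction is worth making because it is specific and costs almost nothing, not because a material bias has been shown.

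**What to change.** In Protocol Section 8.2:

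1. Limit the sentence barring eCRF entry to withdrawal of consent or assent.
2. State that after withdrawal by the investigator or sponsor, AEs, SAEs and drug accountability obtained at the last contact are entered in the eCRF under 9.1.4, 9.2.2 and 5.1.7.1.
3. State that this contact does not replace the EOT visit and the 30-day EOS call where these can be done.

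Do not require a telephone call to be entered as a full EOT assessment: it cannot supply vital signs, and only what was obtained should be recorded.

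The cost is a few sentences at the next amendment. No extra visit is needed and apparently no new form, since the AE and accountability records already exist. Section 8.2 already asks the eCRF to record who made the withdrawal decision, so sites and data management can apply the distinction.
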